As outlined previously, events will be ascertained from several sources including study visits, medical history review, medication review, and retrieval of hospitalization records. The source of events will be accordingly labeled. Poisson regression will be employed to determine key measured factors which predict the incidence of patient safety events. For this analysis, there will be no predetermined primary exposure to be tested in the regression analysis; however, a key analysis will be the relationship between entry GFR and incidence of CKD-PSIs. Other exposures of interest will be examined. The Poisson regression will assume the number of events for each subject follows a Poisson distribution with mean being a product of the length of the follow-up period and the rate of events, where the logarithm of the expected rate of events (per patient-month), is the linear combination of the covariates. We will check whether data display any over-dispersion and may use negative-binomial regression model if over-dispersion is present.

The data will also be structured such that it is possible to explore the relationship between the incidence of CKD-PSIs and key renal endpoints (secondary outcomes). The key adverse secondary outcomes measures to be examined will be 1) hospitalization and, 2) rate of change in renal function, as measured by estimated GFR. For hospitalization, the primary measure will be incidence of unique hospitalizations over the observed patient-months in each group. Comparisons groups will be the patient-months labeled by the prior incidence or absence of CKD-PSIs in a given patient. While an individual without any CKD-PSI during study observation has a hospitalization, that event occurs in the non-PSI group, another individual with at least one CKD-PSI in the study period who has two hospitalizations – one before and the other after the incidence of the CKD-PSI – will contribute two hospitalization events to the data set. The first will be assigned to the non-CKD-PSI group and corresponding to the period from entry to the occurrence of the first CKD-PSI, the second event will be assigned to CKD-PSI group and corresponding to the period from the occurrence of the first CKD-PSI to last follow up time or the end of the study.

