Generalized estimating equations (GEE) with log link function will be employed for examination of the relationship between incidence of CKD-PSIs and hospitalization. GEE will allow for joint modeling of the repeated measures and the incorporation of such a time-varying covariate based in the detection of a CKD-PSI. The effect of ever experiencing CKD-PSI during the study period on the frequency of hospitalization will be displayed by the rate ratio and its 95% confidence interval of hospitalization in PSI group versus non-PSI group.

Estimated GFR will be determined at baseline and at all annual follow-up visits. Since enrollment will be planned to ensure at least one follow-up visit per individual, it will be possible to generate slope estimates for change in renal function in all study participants. Measurement of serum creatinine will be done at a single laboratory to minimize variation in calibration across laboratories, and GFR will be estimated with the modified MDRD equation. Proper transformation will be performed as needed if the distribution of GFR values is skewed. Random effects models will be used to compare change in GFR between those with and without a CKD-PSI. To employ random effects models as a means to compare change in renal function between those participants with and without the incidence of a CKD-PSI and adjust for multiple covariates, the following assumptions will be made:

Each individual will have a separate slope β_i , with an independent intercept α_i , and an error term ϵ_i with mean 0 and a Normal distribution. The residual variance of each slope is assumed to be the same across all individual slopes and the distribution of β_i for participant time assigned to each group is assumed to be a Normal distribution with a mean of b_1 or b_2 corresponding to the two groups (without or with the bracelet/necklace). Similarly, the distribution of individual intercept α_i is assumed to be a Normal distribution with an equal variance across all individuals, and a mean of a_1 or a_2 corresponding to the two groups.

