The random effects model will allow for inclusion of both baseline and time-varying covariates which would include timing of the incidence of the CKD-PSI. In comparison of change in renal function across the two groups (CKD-PSI vs never CKD-PSI), we will test whether the mean slopes b_1 and b_2 are equal, and construct a 95% confidence interval for $d = b_2 - b_1$. For these analyses, we will employ PROC MIXED in SAS V9.1 (SAS Institute Inc., Cary, NC, USA), building on the research group's substantial prior experience using such models and examining changes in renal function.

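### The eGFR-slope means are labelled by bracelet/necklace but tested by CKD-PSI status, and the plan does not say how eGFR values before the first CKD-PSI enter the model

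*Combined protocol and SAP*

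**What the plan says.** All of this is in section 9.I.3, Statistical Analysis.

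- **Purpose of the model:** "Random effects models will be used to compare change in GFR between those with and without a CKD-PSI".
- **Definition of the group means:** each participant has one slope and one intercept. The slope has "a mean of b_1 or b_2 corresponding to the two groups (without or with the bracelet/necklace"), and the intercept has "a mean of a_1 or a_2 corresponding to the two groups".
- **Test:** in comparing "change in renal function across the two groups (CKD-PSI vs never CKD-PSI), we will test whether the mean slopes b_1 and b_2 are equal". A 95% confidence interval for d = b_2 - b_1 follows.
- **Wording that points to a split at the event:** the slope distribution is described "for participant time assigned to each group is assumed to be a Normal distribution", and the model may include "time-varying covariates which would include timing of the incidence of the CKD-PSI".
- **The only explicit assignment rule** concerns a participant hospitalized both before and after an event: "The first will be assigned to the non-CKD-PSI group and corresponding to the period from entry to the occurrence of the first CKD-PSI". It is written for hospitalization and is not repeated for eGFR.

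**The concern.** The same two symbols carry two groupings. The accessory grouping is Phase I against Phase II, 108 against 242 participants. CKD-PSI status divides the cohort differently and changes over time within a participant. Rate of change in eGFR is one of the two key secondary outcomes, and d is the quantity tested for it.

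Once the label is read as CKD-PSI status, the treatment of earlier eGFR values is still open. Assigned participant time and a timing covariate suggest a split. One slope per participant and a never-CKD-PSI group suggest a whole-follow-up comparison. Two competent analysts could fit different PROC MIXED models from this text and report different values of d. If decline before the event is credited to the CKD-PSI group, a real post-event change is diluted. If people with lower or falling eGFR also have more CKD-PSIs, a difference can appear where the events did nothing.

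**Working it through.** **No plan figure to reproduce.** The documents give no effect size, SD or power for the eGFR comparison. Everything below illustrates how far the uncoded choice moves d.

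**Step 1: the two labels are different contrasts.** Accessory: 108 with, 350 - 108 = 242 without. Ever CKD-PSI, using the ends of the Table 4 incidence range (10% to 40% per year) and an assumed constant rate over 1 to 4 years: 350 × 0.10 = 35 ever and 315 never, up to 350 × (1 - 0.6^4) = 305 ever and 45 never.

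**Step 2: how much data the choice touches.** Ascertainment starts 4 months after enrollment. With a constant first-event hazard h and follow-up T, and U = T - 1/3, the mean share of an ever-PSI participant's follow-up that precedes the event is

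(1/3 + 1/h - U·exp(-hU)/(1 - exp(-hU))) / T.

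- h = 0.20, T = 2: (0.333 + 5 - 4.212)/2 = 0.56.
- h = 0.52, T = 4: (0.333 + 1.923 - 0.640)/4 = 0.40.

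So about 40% to 56% of that follow-up is affected.

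**Step 3: why a split in study time also dilutes.** After an event at time u, the added decline is proportional to t - u. If first events were spread evenly from month 4, the mean time since event among those already past it would be (t - 1/3)/2, which rises by only half a year per year. A group line in study time, a_2 + b_2·t, therefore picks up roughly half of a true slope change. This is a heuristic; the simulation follows.

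**Step 4: simulation.** From the documents: 350 participants, annual eGFR, at least one and up to four annual visits, ascertainment from month 4. Assumed: baseline eGFR 40 (SD 12), slope -2 per year (SD 3) independent of baseline, residual SD 4, first-event hazard 0.35 per year at eGFR 40, 1-4 follow-up visits, variance components known, no covariates. Links of 2% and 5% mean that much higher hazard per mL/min of lower eGFR.

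| Model | True -1.0, no link: mean d | SE | No effect, 2% / 5% link: mean d | Rejected |
|---|---|---|---|---|
| Ever/never slope | -0.53 | 0.43 | -0.41 / -0.90 | 16% / 55% |
| Separate lines in study time, split at event | -0.54 to -0.58 | 0.34 | -0.07 / -0.15 | 7% / 8% |
| Time since first CKD-PSI | -0.99 | 0.47 | -0.23 / -0.57 | 8% / 24% |
| Same, plus ever-PSI and ever-PSI-by-time | -0.97 | 0.57 | 0.03 / -0.04 | 5% / 5% |

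The ever/never and time-since rows rest on 1000 runs per setting (Monte Carlo error at most 0.02 on d). The study-time split rests on 300 runs, with 150 more for its dilution. The last two rows have no level indicator.

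- Dilution: 1 - 0.53 = 47% for ever/never; 1 - 0.58 = 42% to 1 - 0.54 = 46% for the study-time split.
- Ratio of mean d to SE at a true -1.0: 0.53/0.43 = 1.2; 0.58/0.34 = 1.7 at best; 0.99/0.47 = 2.1. The larger SE of the time-since term is more than repaid.
- Share of the ever/never bias that the time-since term keeps: 0.23/0.41 = 56% and 0.57/0.90 = 63%.
- With no effect and no link, ever/never gives d = 0.01 (4.6% rejected).
- Adjusting for entry eGFR and its interaction with time does not remove the bias: ever/never -0.42 / -1.01, time since event -0.19 / -0.50.

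**Step 5: a level drop at the event.** With an assumed pure drop of 3 mL/min and no slope change, two separate simulations (300 and 150 runs) gave the time-since term without a level indicator as -0.46 and -0.35, and the sensitivity model as +0.30 and +0.46. With a post-event level indicator the main term is close to zero (about 0.06 in the smaller run), and its SE goes from 0.46 to 0.47.

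**The case against.** The strongest reply is that the parenthesis is a slip that would mislead nobody, and that the rest can be read as a complete model: eGFR before the first event follows a_1 + b_1·t, later eGFR follows a_2 + b_2·t, and PROC MIXED can fit that. Much of this stands. The stated purpose and the test both name CKD-PSI, so a reader should not infer that the plan means to compare eGFR by accessory.

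Nor should a reader infer that the plan ignores timing, or that the words never CKD-PSI commit it to a whole-follow-up comparison. The hospitalization analysis, which is explicitly split, is also summarised as "The effect of ever experiencing CKD-PSI during the study period on the frequency of hospitalization".

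It is also tempting to call a_2 meaningless because nobody is in CKD-PSI time at entry. That does not hold: in a split model a_2 - a_1 is a level-shift parameter, estimable from post-event values. Dropping it for a single intercept would do harm (step 5), since CKD-PSIs include toxic exposures such as contrast agents, for which a drop in level should not be excluded by construction.

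The study-time split also resists the eGFR link better than the time-since term, so the choice is partly a trade-off. What does not stand is the claim that the split reading settles the matter. It is not written down for eGFR, it sits awkwardly with one slope per participant, and it recovers only a little over half of a true slope change.

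**Conclusion.** The label is wrong as written, and that needs no assumptions. The coding of eGFR values before the first CKD-PSI is indicated but not specified. Under the assumed inputs, both readings that the text allows dilute a true post-event slope change by roughly 40-50%.

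The false-positive figures for ever/never coding are doubly conditional: that model would have to be chosen, and lower eGFR would have to raise CKD-PSI risk. The plan treats the relation between entry GFR and CKD-PSI incidence as a question to study and gives no size for it, so a reader should not take the 16% or 55% as a forecast. The SDs and the hazard are single assumed values. The consequence is confined to a key secondary outcome; the primary CKD-PSI incidence analysis is untouched.

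**What to change.** In section 9.I.3:

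1. Replace the bracelet/necklace parenthesis with CKD-PSI status, and say which status is b_2 so that the sign of d is fixed.
2. State that eGFR values before the first CKD-PSI count as non-CKD-PSI time, as the hospitalization rule already does.
3. Specify the fixed effects: time; an indicator for after the first CKD-PSI, which keeps the role of a_1/a_2 as a level shift; time since first CKD-PSI, set to zero before the event and for participants who never have one; and the planned covariates. Define d as the coefficient of time since first CKD-PSI, with its 95% CI.
4. Add one sensitivity run with ever-PSI and ever-PSI-by-time terms, keeping the level indicator, because the main term retains part of any bias from faster decliners having more CKD-PSIs. State that this run estimates a different quantity (the within-participant slope after the event minus that before it), and that its ever-PSI terms use later events and serve only as adjustment.

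Cost: wording, two derived terms and one extra model run, with no new data. Under the assumed inputs with 1-4 visits, the SE of d is about 0.47 (95% half-width 1.96 × 0.47 = 0.92), against 0.43 for ever/never and 0.34 for the study-time split. Power for a true -1.0 is about 56%, computed without the level indicator, which barely changes the SE. The sensitivity run is weaker (SE about 0.57; 40% power without the level indicator). Also, 35-37% of ever-PSI participants would have fewer than two post-event eGFR values, so it should stay secondary.

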Name: v2_Lay Summary

View: v2_Justification, Objective, & Research Design

Justification, Objective, & Research Design

If you uploaded a separate research protocol document in the 'Research Protocol' page, cite the applicable section and page numbers from that document in the answer boxes below.

- 1 * Describe the purpose, specific aims, or objectives of this research. State the hypothesis to be tested:

In this study, 371 individuals with pre-dialysis CKD were consented to achieve a cohort of 350 that proceeded to study procedures with the following objectives:

1) Assess the Tolerability and Efficacy of a Commonly-used Medical Alert Accessory Designed to Increase Recognition of Chronic Kidney Disease (CKD) in a Pilot Sample of Participants from the SAFE KIDNEY CARE COHORT

The first 108 subjects of the Safe Kidney Care cohort (Phase I) were provided a medical alert accessory (choice of bracelet or necklace, stainless steel or sterling silver). Regular contacts were made with Phase I participants to monitor tolerance of medical alert accessory along with the use of a supplemental informational website on best safe practices for patients with CKD, and to measure the frequency of newly-developed Patient Safety Indicators specific to CKD (CKD-PSI).

2) Validate Established CKD-PSIs in a Cohort of Individuals with CKD Tracked Longitudinally

After enrollment in Phase I has concluded, an additional 242 volunteers from the target population were enrolled into the Safe Kidney Care cohort (Phase II) for a total of 350 participants tracked longitudinally to detect the incidence of established CKD-PSIs, assess their measurability, and exam the relationship between the occurrence of these safety events and adverse renal outcomes.

- 2 * Discuss the research design including but not limited to such issues as: probability of group assignment, potential for subject to be randomized to placebo group, use of control subjects, etc.:

Study design: Observational cohort study. Study population: Persons with Stage III – V, pre-dialysis CKD enrolled from a single center (n = 350). The first 108 participants (Phase I) were provided a medical alert accessory (choice of bracelet or necklace).

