Study Measurements: Participants in both Phase I and II underwent baseline and annual in-center visits for medical history and medication review, anthropometric measures, measurement of renal function (serum Cr for estimation of GFR); other laboratory measures, measures of physical function and health literacy, and other questionnaires. Additionally, they had a follow-up telephone call between annual visits to review medications, update contact information, assess for medical events and hospitalizations. Phase I participants also had an assessment of medical alert accessory acceptance and tolerance. The expected duration of study allows up to 4 annual clinic visits and up to 4 mid-year telephone follow-up visits through June 30, 2016. Beginning, July 1, 2016, annual clinic visits stop and will be replaced with just the annual telephone visit up to December 2021. The mid-year telephone follow-up will stop.

Primary outcomes: CKD-PSIs including medication errors (such as NSAIDs, improperly dosed meds), toxic exposures (such as contrast agents), and medical events (such as hyperkalemia or hypoglycemia); Secondary outcomes: including changing renal function, hospitalization, ESRD, and death. Phase I participants were followed for acceptance and tolerance of medical alert accessory.

- 3 * Describe the relevant prior experience and gaps in current knowledge. Describe any relevant preliminary data:
Refer to Protocol item 5. BACKGROUND

- 4 * Provide the scientific or scholarly background, rationale, and significance of the research and how it will add to existing knowledge:

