300 \pm 3.3% \pm 4.7% \pm 5.3% \pm 5.7%

- 2 * Provide the plan for data analysis. Include in the description the types of comparisons that are planned (e.g., comparison of means, comparison of proportions, regressions, analysis of variance, etc.), which is the primary comparison/analysis, and how the analyses proposed will relate to the primary purposes of the study:

From Protocol:

9.I.3. Statistical Analysis

The purpose of this analysis will be to measure the incidence of the CKD-PSIs in the study cohort and to determine the adjusted incidence rates across key factors which relate to safety in CKD. Event ascertainment will begin 4 months (with first telephone follow-up) after enrollment at which time individual events will be recorded longitudinally and cumulatively.

We will consider each specific type of event as an endpoint, but the primary analysis will be based on a composite endpoint of all CKD-PSIs endorsed for inclusion in the trial. The incidence of the events will be expressed per patient-months accrued for all participants in the study cohort and cumulative incidence rates will be determined for both the composite and individual events. Each event will be recorded per individual at the time of the event. For example, if there was an episode of hypoglycemia documented in April for a participant enrolled in January, and an exposure to NSAID in December, then that individual will have 2 CKD-PSI events per 12 patient-months.

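### The ever/never CKD-PSI comparison of GFR slopes lets GFR loss itself place fast progressors in the CKD-PSI group; the size of this bias cannot be fixed from the documents

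*Combined protocol and SAP*

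**What the plan says.** Section 9.I.3 (Sample Size and Data Analysis, item 2) describes the slope analysis in three steps.

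- The grouping: "Random effects models will be used to compare change in GFR between those with and without a CKD-PSI".
- The model: "Each individual will have a separate slope", with a random intercept. Baseline and time-varying covariates are allowed, "which would include timing of the incidence of the CKD-PSI".
- The test: "In comparison of change in renal function across the two groups (CKD-PSI vs never CKD-PSI), we will test whether the mean slopes" are equal, with a 95% confidence interval for their difference.

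The primary outcomes (Justification, Objective, & Research Design, item 2) are "CKD-PSIs including medication errors (such as NSAIDs, improperly dosed meds), toxic exposures (such as contrast agents), and medical events (such as hyperkalemia or hypoglycemia"). For incidence, "the primary analysis will be based on a composite endpoint of all CKD-PSIs endorsed for inclusion in the trial". The slope paragraphs name no subset of CKD-PSIs. Section 9.I.3 also says that "a key analysis will be the relationship between entry GFR and incidence of CKD-PSIs".

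For hospitalization, the same section divides each person's time at the first CKD-PSI and assigns events before and after it to different groups. The slope paragraphs contain no such rule, and no lag, landmark or mention of reverse causation. They do speak of assigning participant time to groups, but they describe the two groups as without and with the bracelet or necklace, which conflicts with the test stated next.

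**The concern.** The outcome is GFR decline, and the exposure is an event recorded while that decline is under way. Hyperkalemia is likely to become more frequent as GFR falls. If a dosing error is judged against kidney function, an unchanged dose can become a CKD-PSI because GFR fell. A person who declines quickly then has more chance of being labelled, and the label marks the decline instead of causing it.

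Objective 2 asks how CKD-PSIs relate to adverse renal outcomes, and the overall hypothesis is that they contribute to them. A steeper slope in the CKD-PSI group would be read as support, yet it is also what reverse causation would produce. Change in renal function is one of the two key secondary outcomes, so the comparison is likely to be reported.

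**Working it through.** **Plan's own figures.** No power, effect size or slope variance is given for this comparison. The only sample-size figures are the precision values in Table 4. At n = 250 and 10% incidence, 1.96 × √(0.10 × 0.90 / 250) = 3.7 points, against ±3.6 stated. They have no bearing on this point.

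**Inputs from the documents.** The cohort is 350 ("for a total of 350 participants tracked longitudinally"). eGFR is measured at baseline and annually, with up to 4 annual visits. Table 4 spans CKD-PSI incidence of 10-40% per year. Slopes differ between people.

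**Assumed inputs.** Entry GFR 40 (SD 12, limited to 15-60), mean slope -2 mL/min/yr, slope SD 2.5, residual SD 4, eGFR at years 0 to 4. The CKD-PSI rate ratio (RR) per 10 mL/min lower current GFR is varied. A CKD-PSI never changes GFR.

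**Mechanism by hand.** Let G(t) = a + s·t and λ(t) = λ₀·exp{γ(40 - G(t))/10}. Then P(ever) = 1 - exp(-∫λ dt). Take λ₀ = 0.20 per year, γ = 0.4 (RR 1.49), 4 years, and two equal-sized types who both enter at GFR 40, with slopes one SD either side of -2.

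- Slope -4.5: ∫λ = 0.20 × (e^0.72 - 1)/0.18 = 1.17, so P(ever) = 0.690.
- Slope +0.5: ∫λ = 0.20 × (1 - e^-0.08)/0.02 = 0.769, so P(ever) = 0.536.
- Share of fast decliners among ever: 0.690/(0.690 + 0.536) = 0.563. Among never: 0.310/(0.310 + 0.464) = 0.401.
- False slope difference: -5 × (0.563 - 0.401) = -0.81 mL/min/yr.

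Entry GFR is identical here, so adjusting for it cannot remove the difference. The full simulation agrees: -0.80 with baseline GFR × time in the model, -0.72 without.

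**Simulation, ever/never contrast, true effect zero** (600 replicates, random intercept and slope; ranges are over rates of 10-40% per year unless stated).

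| Setting | False difference (mL/min/yr) | p<0.05 |
|---|---|---|
| Risk unrelated to GFR | about 0 | about 6% |
| RR 1.22, all events | -0.31 to -0.49 | 18-25% |
| RR 1.49, all events | -0.62 to -0.92 | 54-66% |
| RR 2.01, all events | -1.01 to -1.24 | 91-94% |
| RR 1.49-2.01, half of events | -0.37 to -0.84 | 21-64% |
| RR 1.49, rate 20%, slope SD near 0 | 0.00 | 5% |
| RR 1.49, rate 20%, slope SD 1.5 | -0.26 | 24% |
| RR 1.49, rate 20%, slope SD 4 | -1.79 | 97% |

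**A second set of assumptions.** Entry eGFR 40 (SD 13, limited to 12-60), slope SD 3, residual SD 3, 2-5 eGFRs per person, and a CKD-PSI chance per visit of 7%, 13% or 30% at eGFR ≥45, 30-44 or <30.

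- Gradient applied to all events: -0.83 to -0.88 and 56-65% over repeated runs.
- Half the risk GFR-driven: about -0.44, 18-20%. One third: about -0.27, 10%.
- Milder gradient (11/14/20%): -0.35, 16%. Slope SD 1.5: about -0.28, 19-21%.

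**Time split at the first CKD-PSI.** Under the first set, post-event state × time gives -0.05 to -0.26 (4-21%), and a change of slope after the event (RR 1.49) gives -0.14 to -0.46 (13-24%). Under the second set, results run from -0.04 to -0.29 (2-9%).

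**Remedies, first set.** A landmark (CKD-PSI in year 1, slope over years 2-4, adjusted for baseline GFR and prior GFR change) gives -0.05 to +0.03 (4-8%). Grouping only on events unrelated to GFR gives a difference within ±0.03 (4-7%).

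**The case against.** The strongest reply is that the plan already lets CKD-PSI timing enter the model and splits time for hospitalization, so a sensible analyst would do the same for slopes. Much of this stands: a time split removes most of the bias. A reader might infer that timing makes no difference because a fast progressor stays steep after being labelled; the calculations do not support that. But the plan says only that the model permits timing, and its next sentence states the test as ever against never.

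A second reply is that the GFR dependence is not documented. This also stands. The CKD-PSI definitions come from separate work and are not included, so it is an inference that dosing errors are judged against GFR. A reader might take the entry-GFR analysis as the plan's admission that CKD-PSIs rise as GFR falls. It plans to examine that relationship and states no direction, and entry GFR is not GFR decline.

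Third, NSAID and contrast exposure need not depend on GFR and would dilute the bias. That is right, and the half and one-third rows show by how much; some bias remains in each.

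Finally, this is a secondary, exploratory analysis. The primary incidence estimate and its precision are unaffected.

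**Conclusion.** The point holds for the contrast as the plan words it. With no true effect, the ever/never comparison shows a steeper CKD-PSI slope whenever CKD-PSI risk rises as GFR falls and slopes vary between people. The plan's model assumes the second condition; the first is likely but inferred.

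The size is not determined by the documents. Across most assumptions tried, the false difference is about -0.25 to -1.2 mL/min/yr, with p<0.05 in about 10% to over 90% of runs. It vanishes if slopes barely differ and is larger (-1.79) at a slope SD of 4. A reader might quote a single false-positive rate near 65% as the study's error rate. That figure belongs to one steep gradient applied to every CKD-PSI, and the documents do not support it as an estimate. Splitting time at the first CKD-PSI leaves about 0 to -0.5 mL/min/yr and 2-24% rejection, in the same direction.

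The change should be made before analysis, but it does not threaten the primary aim.

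**What to change.** In 9.I.3:

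1. Replace the ever/never slope test with one in which the CKD-PSI precedes the slope. Either divide participant time at the first CKD-PSI, as is already done for hospitalization, or use a landmark: CKD-PSI in an early window, slope afterwards, adjusted for baseline GFR and prior GFR change. Both keep the full composite, which Objective 2 needs. Given the residual bias after a time split, the landmark is the better check.
2. Before analysis, code each endorsed CKD-PSI as GFR-dependent or not, with a written reason. Treat hypoglycemia as GFR-dependent, because Study Procedures, item 1, ties its risk to diminished kidney function. Do not assume NSAID or contrast exposure to be independent without stating why.
3. Pre-specify the slope comparison on the events judged not GFR-dependent as a companion analysis.
4. Report any ever/never composite comparison as descriptive, stating that GFR loss can itself produce CKD-PSIs.
5. Reconcile the two descriptions of the slope groups (bracelet or necklace against CKD-PSI).

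The cost is SAP wording and one coding variable on events already recorded. There will be fewer exposed participants or less exposed time, and a wider interval. A landmark also loses late entrants: enrollment ran to 2014 and clinic visits stopped on July 1, 2016, so some people have few eGFRs after an early window.
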